10.1.10. Publication Policy

- The primary publication should be published by the sponsor prior to any other investigator-initiated publications, manuscripts, abstracts, or presentations.
- The results of this trial may be published or presented at scientific meetings. If this is foreseen, the investigator agrees to submit all manuscripts or abstracts to the sponsor before submission. This allows the sponsor to protect proprietary information and to provide comments.
- The sponsor will comply with the requirements for publication of trial results. In accordance with standard editorial and ethical practice, the sponsor will generally support publication of multicenter studies only in their entirety and not as individual site data. In this case, a coordinating investigator will be designated by mutual agreement.
- Authorship will be determined by mutual agreement and in line with International Committee of Medical Journal Editors authorship requirements.

10.2. Appendix 2: AEs and SAEs: Definitions and Procedures for Recording, Evaluating, Follow-up, and Reporting

10.2.1. Definition of AE

AE Definition

• An AE is any untoward medical occurrence in a clinical trial subject, temporally associated with the use of IMP, whether or not considered related to the IMP.• NOTE: An AE can therefore be any unfavorable and unintended sign (including an abnormal laboratory finding), symptom, or disease (new or exacerbated) temporally associated with the use of IMP.
Events Meeting the AE Definition

• Any abnormal laboratory test results (hematology, clinical chemistry, or urinalysis) or other safety assessments (e.g., ECG, radiological scans, vital signs measurements), including those that worsen from baseline, considered clinically significant in the medical and scientific judgment of the investigator (i.e., not related to progression of underlying disease).• Exacerbation of a chronic or intermittent pre-existing condition including either an increase in frequency and/or intensity of the condition.• New condition detected or diagnosed after IMP administration even though it may have been present before the start of the trial.• Signs, symptoms, or the clinical sequelae of a suspected intervention-intervention interaction.• Signs, symptoms, or the clinical sequelae of a suspected overdose of either IMP or a concomitant therapy. Overdose to be reported as an AE/SAE.• Lack of efficacy or failure of expected pharmacological action per se will not be reported as an AE or SAE. Such instances will be captured in the efficacy assessments. However, the signs, symptoms, and/or clinical sequelae resulting from lack of efficacy will be reported as AE or SAE if they fulfill the definition of an AE or SAE.
Events NOT Meeting the AE Definition

• Medical or surgical procedure (e.g., endoscopy, appendectomy): the condition that leads to the procedure is the AE.• Situations in which an untoward medical occurrence did not occur (social and/or convenience admission to a hospital).• Anticipated day-to-day fluctuations of pre-existing disease(s) or condition(s) present or detected at the start of the trial that do not worsen.

10.2.2. Definition of SAE

An SAE is defined as any untoward medical occurrence that, at any dose, meets one or more of the criteria listed:

a. Results in death

b. Is life threatening

The term *life threatening* in the definition of *serious* refers to an event in which the subject was at risk of death at the time of the event. It does not refer to an event, which hypothetically might have caused death, if it were more severe.

c. Requires inpatient hospitalization or prolongation of existing hospitalization

- In general, hospitalization signifies that the subject has been admitted (usually involving at least an overnight stay) at the hospital or emergency ward for observation and/or treatment that would not have been appropriate in the physician's office or outpatient setting. Complications that occur during hospitalization are AEs. If a complication prolongs hospitalization or fulfills any other serious criteria, the event is serious. When in doubt as to whether hospitalization occurred or was necessary, the AE should be considered serious.
- Hospitalization for elective treatment of a pre-existing condition that did not worsen from baseline is not considered an AE.

d. Results in persistent or significant disability/incapacity

- The term *disability* means a substantial disruption of a person's ability to conduct normal life functions.
- This definition is not intended to include experiences of relatively minor medical significance such as uncomplicated headache, nausea, vomiting, diarrhea, influenza, and accidental trauma (e.g., sprained ankle) that may interfere with or prevent everyday life functions but do not constitute a substantial disruption.

e. Is a congenital anomaly/birth defect

f. Other situations:

- Medical or scientific judgment should be exercised by the investigator in deciding whether SAE reporting is appropriate in other situations such as significant medical events that may jeopardize the subject or may require medical or surgical intervention to prevent one of the other outcomes listed in the above definition. These events should usually be considered serious.
 - Examples of such events include invasive or malignant cancers, intensive treatment for allergic bronchospasm, blood dyscrasias, convulsions or development of intervention dependency or intervention abuse.

10.2.3. Recording and Follow-Up of AE and/or SAE

AE and SAE Recording

- AEs will be collected from signing the ICF. AEs occurring after first IMP intake will be considered treatment-emergent adverse events (TEAEs) in the statistical analysis.
- A pre-existing medical condition should be reported as an adverse event if the condition increases in severity (e.g. from mild to moderate).
- At each visit the subject should be asked about AEs in an objective manner, *e.g.*: “Have you experienced any problems since the last visit?”.
- Only medically qualified personnel (investigators) must assess AEs.
- When an AE/SAE occurs, it is the responsibility of the investigator to review all documentation (e.g., hospital progress notes, laboratory reports, and diagnostics reports) related to the event.
- The investigator will then record all relevant AE/SAE information.
- It is **not** acceptable for the investigator to send photocopies of the subject’s medical records to the sponsor or designee in lieu of completion of the SAE form.
- There may be instances when copies of medical records for certain cases are requested by the sponsor or designee. In this case, all subject identifiers, with the exception of the subject number, will be redacted on the copies of the medical records before submission to the sponsor or designee.
- The investigator will attempt to establish a diagnosis of the event based on signs, symptoms, and/or other clinical information. Whenever possible, the diagnosis (not the individual signs/symptoms) will be documented as the AE/SAE.
- All AEs should be followed until they have reached a final outcome (Recovered/resolved, recovering/ resolving, recovered/resolved with sequelae) or the subject’s participation in the trial ends, whichever comes first.
- SAEs and non-serious AEs considered related to IMP treatment should be followed on a regular basis according to the investigator’s clinical judgment until a final outcome has been established.
- The outcome “recovering” can be used as the final outcome for events that are stabilized (in essence no further worsening is expected) and expected by the investigator to resolve over time.
The outcome “not resolved” can be used as the final outcome for events that are not expected to resolve over time (e.g. cancer).

Assessment of Intensity

The investigator will make an assessment of intensity for each AE and SAE reported during the trial and assign it to one of the following categories:

- Mild: Awareness of symptoms, sign, illness, or event that is easily tolerated.
- Moderate: Discomfort sufficient to interfere with usual activities.
- Severe: Incapacitating with inability to work or undertake further normal activities.

Note the distinction between seriousness and severity: The term severe is used to describe the intensity of the event and a severe event is not necessarily serious. A severe headache would probably not constitute a SAE whilst a mild myocardial infarction likely would constitute a SAE. The seriousness criteria serve as a guide for defining regulatory reporting obligations.

Assessment of Causality

- The investigator is obligated to assess the relationship between IMP and each occurrence of each AE/SAE. The investigator will use clinical judgment to determine the relationship.
- A *reasonable possibility* of a relationship conveys that there are facts, evidence, and/or arguments to suggest a causal relationship, rather than a relationship cannot be ruled out.
- Alternative causes, such as underlying disease(s), concomitant therapy, and other risk factors, as well as the temporal relationship of the event to IMP administration, will be considered and investigated.
- The investigator will also consult the IB and/or product information, for marketed products, in his/her assessment.
- There may be situations in which an SAE has occurred and the investigator has minimal information to include in the initial report to sponsor or designee. However, it is very important that the investigator always makes an assessment of causality for every event before the initial transmission of the SAE data to sponsor or designee.
- The investigator may change his/her opinion of causality when new follow-up information is available and send an SAE follow-up report with the updated causality assessment.
- The causality assessment is one of the criteria used when determining regulatory reporting requirements.
- The relationship will be characterized using the following causality ratings:
 - Related: There is a reasonable possibility that the AE was caused by the IMP treatment. There is a reasonable time relationship to IMP treatment intake. The AE cannot be explained by disease or other drugs. There may or may not be information about de-challenge or re-challenge. Disappearance of the AE upon de-challenge supports this category. Reappearance upon re-challenge is strongly supportive.


○ Not related: There is no reasonable possibility that the event was caused by the IMP. The temporal relationship to drug administration makes a causal relationship improbable or other drugs or underlying disease or conditions provide plausible explanations.○ Not applicable: This assessment can be used e.g., in cases where the subject did not receive any treatment with IMP
--

Outcome

The Investigator is obliged to record the most appropriate outcome using the following categories:

- Recovered/resolved
- Recovering/resolving
- Not recovered/not resolved/ongoing
- Recovered/resolved with sequelae
- Fatal
- Unknown

Follow-up of AEs and SAEs

- The investigator is obligated to perform or arrange for the conduct of supplemental measurements and/or evaluations as medically indicated or as requested by sponsor or designee to elucidate the nature and/or causality of the AE or SAE as fully as possible. This may include additional laboratory tests or investigations, histopathological examinations, or consultation with other health care professionals.
- The investigator will submit any updated SAE data to sponsor or designee within 24 hours of receipt of the information.

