CRP was initially selected as the primary endpoint because CRP has been reported to predict severe disease ([Tan et al., 2020](#); [Wang, 2020](#)) and mortality ([Ruan et al., 2020](#)) in COVID-19. However, there was a rapid and profound decrease in CRP in both the C21 and the placebo group, most likely because the patients were treated with glucocorticoids which became part of standard of care at the time of trial initiation likely leading to no statistical difference in the primary endpoint CRP. Nevertheless, in the patients with more pronounced respiratory distress with need of supplementary oxygen at baseline, there was a small but significantly greater reduction of CRP in the C21 than in the placebo group.

There were 64 treatment-emergent AEs reported by 60.8% of the patients in the C21 group and 90 events reported by 67.3% of the patients in the placebo group. Most events were mild, and no event in either group was classified as related to trial treatment by the investigators. The most frequent AE was hyperglycemia, which occurred more frequently in the C21 group than in the placebo group. The level of hyperglycemia was predominantly mild and not reported as related to C21 by investigators.

Taken together, C21 on top of standard of care, including glucocorticoids and remdesivir, significantly improved respiratory function reflected by a reduced need for supplemental oxygen in hospitalized COVID-19 patients.

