10.1.5. Committees Structure

10.1.5.1. Data Monitoring Committee

An independent DMC will be established. The functions and responsibilities of the DMC will be described in a DMC charter.

Throughout the duration of the trial, the DMC will evaluate all SUSARs on an ongoing basis. The DMC is scheduled to meet twice during trial conduct, to review unblinded safety data from the trial after data collection for 15 days on the first 25% of randomized subjects, and to review safety and efficacy data after data collection for 15 days on the first 50% of randomized subjects. In addition, the DMC members may call for an *ad hoc* safety review meeting at any time during the trial. This may include a review of unblinded safety data after data collection for 15 days on the first 75% of randomized subjects. The DMC will provide appropriate written recommendations to the sponsor regarding trial continuation, protocol modifications or trial suspension. The DMC will operate unblinded and independent from all sites, CRO, vendor and sponsor staff involved in the conduct of the trial.

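### The Related category rules out any event that disease or other drugs could explain, which conflicts with the protocol's own reasonable-possibility standard and may under-classify related events and SUSARs

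*Protocol*

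**What the plan says.** Protocol 10.2.3, under the assessment of causality, offers three ratings.

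- **Related** opens with "There is a reasonable possibility that the AE was caused by the IMP treatment". It asks for a reasonable time relationship and then states "The AE cannot be explained by disease or other drugs". Information on de-challenge or re-challenge is expressly optional.
- **Not related** opens with the absence of a reasonable possibility. It then gives two grounds: an improbable time relationship, or that "other drugs or underlying disease or conditions provide plausible explanations".
- **Not applicable** is not a middle level: "This assessment can be used e.g., in cases where the subject did not receive any treatment with IMP".

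The same section says that a reasonable possibility "conveys that there are facts, evidence, and/or arguments to suggest a causal relationship, rather than a relationship cannot be ruled out". Alternative causes are to be considered and investigated, and "The investigator will use clinical judgment to determine the relationship".

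On use of the rating, 10.2.3 makes causality one criterion for regulatory reporting. Protocol 10.1.5.1 says "the DMC will evaluate all SUSARs on an ongoing basis". SAP 12.6.1 tabulates related TEAEs, related SAEs and related AEs leading to death.

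**The concern.** The general standard asks whether there is positive evidence of a drug cause. It does not ask the investigator to exclude every other cause. The extra condition under Related does ask that, and the ground under Not related lets a merely plausible alternative count against the drug. With no intermediate rating, an investigator who sees both a reason to suspect C21 and another possible cause must choose between two definitions that each fit only in part.

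The choice has consequences beyond a table cell:

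- It feeds expedited reporting, and through SUSARs it feeds the only ongoing review of individual event reports that the documents assign to the DMC.
- Under 10.2.3 it helps decide which non-serious AEs are followed to a final outcome.
- Under 8.5.1 an SAE learned of after a subject's participation has ended must be notified only if the investigator considers it reasonably related to the product or to trial participation.
- It populates the related-event tables in SAP 12.6.1.

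**Working it through.** The plan gives no figure to reproduce. The check is to apply the two definitions to the possible cases, assuming that the timing is reasonable.

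| Evidence of an IMP cause | Plausible alternative cause | Related | Not related |
|---|---|---|---|
| Yes | No | all conditions met | lead condition fails |
| No | Yes | lead condition fails | lead condition and a listed ground met |
| Yes | Yes | lead condition met, exclusion condition fails | lead condition fails, a listed ground met |

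The first two rows are settled. The third is not. If every sentence of a definition is required, the event meets neither rating. If any one sentence is enough, it meets both. No consistent reading gives one answer. The general standard would: evidence suggesting causation is present, so the event is related.

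**Does the third row arise in this trial?** Inclusion criterion 3 (Protocol 5.1) admits only inpatients on supplemental oxygen, non-invasive ventilation or high-flow oxygen. Appendix 4 (10.4) allows standard of care that includes remdesivir, dexamethasone, tocilizumab, convalescent plasma and monoclonal antibodies. In the phase 2 trial (2.2) most patients received glucocorticoids and 67.0% received remdesivir. An explanation by disease or another drug will often be available.

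**A case that the protocol itself anticipates.** The risk table in 2.3.1 says that clinically relevant interactions with CYP enzymes and efflux transporters cannot be excluded. Section 10.2.1 makes the sequelae of suspected interactions reportable as AEs. If C21 raised exposure to a co-medication and toxicity followed, another drug would explain the event. Taken literally it would fail the Related definition although C21 contributed.

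**What does not depend on the rating.**

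- All SAEs go to the sponsor within 24 hours of awareness (Protocol 8.5.1).
- The DMC reviews unblinded safety data after the first 150 randomized subjects (Protocol 1.1; SAP 8.0). Protocol 10.1.5.1 instead gives two meetings, at 25% and 50%; with 300 subjects these fall at 0.25 × 300 = 75 and 0.50 × 300 = 150. The review at 150 is common to both schedules. The DMC may also meet ad hoc at any time.
- SAP 12.6.1 gives by-arm risk differences with 95% confidence intervals for any TEAE, SAEs, severe TEAEs, discontinuations and fatal TEAEs, and tables of all TEAEs and SAEs by system organ class and preferred term.
- SAP 10.6 counts a missing relationship as related. This gives no help once Not related has been entered.

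**The case against.** The strongest reply is that reasonable possibility leads both definitions, that the final call is clinical judgment, and that alternative causes are to be weighed, not excluded. On that view the extra sentence is loose drafting that sensible investigators will read in context. In a placebo-controlled trial the by-arm comparison detects a drug effect whatever the rating.

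Much of this stands, and it rules out three stronger readings that a reader might draw.

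1. *That almost no event can be Related and the SUSAR flow to the DMC is cut off.* Investigator causality is one criterion among several, and every SAE reaches the sponsor. The documents neither describe nor exclude a sponsor causality assessment. The DMC charter and Safety Management Plan are not available here. An event unlike COVID-19 or its treatment, such as the alopecia seen at a higher dose (2.3.1), could still be rated Related.
2. *That an event with two possible causes fails Related and squarely meets Not related.* It fails the lead sentence of Not related. The result is ambiguity with a pull towards Not related, not a rule that compels it.
3. *That phase 2 shows the effect.* Protocol 2.2 reports 64 TEAEs on C21 and 90 on placebo, 64 + 90 = 154, and "no event in either group was classified as related to trial treatment by the investigators". Nothing says that phase 2 used this wording. The 90 placebo events cannot have been caused by C21, and zero also fits a well-tolerated drug. Even 0 of 64 is compatible with a related share of up to 1 − 0.05^(1/64) = 4.6% (one-sided 95% limit, treating events as independent).

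What the reply does not remove is the contradiction. Clinical judgment cannot be applied consistently across sites when the wording supports either rating.

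**Conclusion.** The point holds as an internal conflict. The exclusion condition under Related, and the unqualified alternative-explanation ground under Not related, are both at odds with the section's own standard. Events with evidence of a C21 cause and a plausible alternative may be under-classified. That can lower the number of SUSARs sent to the DMC and weaken the related TEAE and SAE tables.

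The size cannot be estimated, because the documents do not say how often both conditions will occur together or how investigators will resolve them. The conclusion assumes that sites apply the definitions roughly as written and that no unseen document overrides them. The main safety comparison between arms is not at risk. The exposure is in individual-case signals between scheduled DMC reviews and in the reading of the related-event tables. This is worth correcting because the change is small.

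**What to change.** In Protocol 10.2.3:

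1. Delete the sentence "The AE cannot be explained by disease or other drugs" from Related.
2. In Not related, let a plausible alternative explanation count only when there is also no reasonable possibility that the IMP caused the event.
3. State that an event with a reasonable possibility of an IMP cause is Related even when another cause is also possible.

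Align the CRF guidance, tell sites by memo, and apply the change prospectively. If earlier SAEs are re-assessed, do it blinded, before database lock, and for all SAEs. Revisiting only those coded Not related could move ratings in one direction only. The memo would need to authorize any re-assessment expressly, because 10.2.3 ties a change of causality opinion to new follow-up information.

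The cost is an edit to Appendix 2, the CRF guidance and a site memo. The downside is somewhat more events coded related and more expedited reports. Without a re-assessment, ratings before and after the change rest on different wording, and the trial report should say so.

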10.2.4. Reporting of SAEs

SAE Reporting to the sponsor or designee via an Electronic Data Collection Tool

- The primary mechanism for reporting an SAE to the sponsor or designee will be the electronic data collection tool.
- If the electronic system is unavailable, then the site will use the paper SAE data collection tool to report the event within 24 hours.
- The site will enter the SAE data into the electronic system as soon as it becomes available.
- After the trial is completed at a given site, the electronic data collection tool will be taken offline to prevent the entry of new data or changes to existing data.
- If a site receives a report of a new SAE from a trial subject or receives updated data on a previously reported SAE after the electronic data collection tool has been taken

offline, then the site can report this information on a paper SAE form or to the sponsor or designee by telephone.

- Contacts for SAE reporting can be found in the Safety Management Plan provided to the sites.

